7.3.2 Regulatory Reporting for Studies Conducted Under DMID-Sponsored IND

Following notification from the site PI or appropriate sub-investigator, DMID, as the IND sponsor, will report any suspected unexpected serious adverse reaction (SUSAR) and any SAEs related to study products to the FDA and will notify all site PI's (i.e., all PI's to whom the sponsor is providing drug) under its IND(s) or under any PI's IND(s) of potential serious risks from clinical studies or any other source, as soon as possible. DMID will report to the FDA any SUSAR and related SAEs that are fatal or life-threatening as soon as possible, but in no case later than 7 calendar days after the sponsor's initial receipt of the information. If the related SAE is not fatal or life-threatening the IND safety report will be submitted within 15 calendar days after the sponsor determines that the information qualifies for reporting as specified in 21 CFR Part 312.32. Relevant follow up information to an IND safety report will be submitted as soon as the information is available. Upon request from FDA, DMID will submit to the FDA any additional data or information that the agency deems necessary, as soon as possible, but in no case later than 15 calendar days after receiving the request.

All SAEs designated as “not related” to study product(s), will be reported to the FDA at least annually in a summary format.

7.3.3 Reporting of Pregnancy

Pregnancy is not an AE but is a collectible event. Pregnancies occurring in study subjects will be reported in IDES (internet data entry system). With the subject’s permission, all study mandated samples will be collected, and the subject will continue in follow-up for safety events. Efforts will be made to follow all pregnancies reported during the study to pregnancy outcome with the subject’s permission.

7.4 Type and Duration of Follow-up of Subjects after Adverse Events

All adverse and serious adverse events will be followed to resolution or until determined to be stable.

AEs will be assessed and followed from initial recognition of the AE through end of the protocol defined follow-up period.

SAEs will be followed up through resolution even if duration of follow-up goes beyond the protocol-defined the follow-up period.

Resolution of an AE is defined as the return to pre-treatment status or stabilization of the condition with the expectation that it will remain chronic.

7.5 Procedures to be followed in the Event of Abnormal Laboratory Test Values or Abnormal Clinical Findings

The site PI or appropriate sub-investigator is responsible for recording all AE/SAEs that are observed or reported during this trial, regardless of the relationship to study product. AE/SAEs, abnormal laboratory test values, or abnormal clinical findings will be collected, assessed, documented, reported, and followed appropriately. Grading of the laboratory AEs will be based on the toxicity table.

7.6 Halting Rules

7.6.1 Sentinel Halting Criteria

Sentinel subject safety data (from day 1 of the dosing of the first Sentinel through day 7 post-dosing of the last Sentinel, for every dose) will be reviewed. Further study enrollment and dosing will be halted for SMC review/recommendation if any Halting Rules (listed below) are met from the time of the first study vaccination through the end of the first reactogenicity period (Day 8) at any dose for any sentinel participant.

- Death of an enrolled subject or any SAE if the SAE is considered related to the investigational products.
- Any Grade 3 unsolicited AE related to the investigational products.
- Any Grade 3 solicited AE. The size (as measured in mm) of erythema, ecchymosis, and induration/swelling will not be used as a halting criterion.

7.6.2 Cohort Halting Rules

Further study enrollment and dosing will be halted for SMC review/recommendation if any of the following Halting Rules are met after administration of any dose of study product within a cohort.

- Death of an enrolled subject or any SAE that is considered by the Medical Monitor to be related to the investigational products.
- Two (2) or more subjects in the same cohort experience the same or similar Grade 3 unsolicited AE (including but not limited to the same parameter or next level of coding in the Medical Dictionary for Regulatory Activities (MedDRA) hierarchy, High Level Term per the MedDRA current version) related to the investigational products.
- Two (2) or more subjects in the same cohort experience the same Grade 3 solicited AE. The size (as measured in mm) of erythema, ecchymosis, and induration/swelling will not be used as a halting criterion.

In the case of a halting rule being met due to Grade 3 solicited AEs in the CJCV2+adjuvant group, the cohort could proceed with CJCV2 alone for the following or remaining of the Cohorts (Cohorts 2 and/or 3) after review of the SMC.

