7.1.1.1 Adverse Events Grading

All AEs (laboratory and clinical symptoms) will be graded for severity and assessed for relationship to study product (see definitions). AEs characterized as intermittent require documentation of onset and duration of each episode. The start and stop date of each reported AE will be recorded on the appropriate eCRF. Changes in the severity of an AE will be documented to allow an assessment of the duration of the event at each level of intensity.

Severity of Event:

AEs will be assessed by the investigator using a protocol-defined grading system (toxicity table included as [Appendix B](#)). For events not included in the protocol-defined grading system, the following guidelines will be used to quantify severity:

- Mild (Grade 1): Events that are usually transient and may require only minimal or no treatment or therapeutic intervention and generally do not interfere with the subject's usual activities of daily living.
- Moderate (Grade 2): Events that are usually alleviated with additional specific therapeutic intervention. The event interferes with usual activities of daily living, causing discomfort but poses no significant or permanent risk of harm to the research participant.
- Severe (Grade 3): Events interrupt usual activities of daily living, or significantly affects clinical status, or may require intensive therapeutic intervention. Severe events are usually incapacitating.

Relationship to Study Product: The assessment of the AE's relationship to study product will be done by the study clinician licensed to make medical diagnoses and listed on the Form FDA 1572 as the site PI or sub-investigator. Whether the AE is related or not, is not a factor in determining what is or is not reported in this trial. If there is any doubt as to whether a clinical observation is an AE, the event should be reported.

In a clinical trial, the study product must always be suspect. The relationship to study product will be assessed for AEs using the terms related or not related:

- Related – There is a reasonable possibility that the study product caused the AE. Reasonable possibility means that there is evidence to suggest a causal relationship between the study product and the AE.
- Not Related – There is not a reasonable possibility that the administration of the study product caused the event.

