7.6.3 Study Halting Criteria

Further study enrollment and dosing will be halted for SMC review/recommendation if any of the following Halting Rules are met after administration of any dose of study product.

- Death of an enrolled subject or any SAE if the SAE is considered by the Medical Monitor to be related to the investigational products.
- Three (3) or more subjects experience the same or similar Grade 3 unsolicited AE (including but not limited to the same parameter or next level of coding in the MedDRA hierarchy, High Level Term per the MedDRA current version) related to the investigational products.

Three (3) or more subjects experience the same Grade 3 solicited AE. The size (as measured in mm) of erythema, ecchymosis, and induration/swelling will not be used as a halting criterion

If a halting rule is met, a thorough review of the event will be undertaken by the investigators and the SMC. Vaccination may be resumed with the concurrence of the SMC, sponsor's representative, and the PI.

The study may also be suspended because of safety findings such as an overall pattern of symptomatic, clinical, or laboratory events that the Medical Monitor considers related to the study products and that may appear minor in terms of individual events, but that may collectively represent a serious potential concern for safety

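### After a single non-fatal SAE outside the sentinel window, the automatic halt depends on the sponsor's Medical Monitor alone, although the protocol assigns SAE relatedness to the site physician

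*Protocol*

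**What the plan says.** The SAE bullets at the three halting levels differ in whose judgement counts:

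- Sentinels (7.6.1): "Death of an enrolled subject or any SAE if the SAE is considered related to the investigational products". No assessor is named.
- Cohort (7.6.2): "Death of an enrolled subject or any SAE that is considered by the Medical Monitor to be related to the investigational products".
- Study (7.6.3): "Death of an enrolled subject or any SAE if the SAE is considered by the Medical Monitor to be related to the investigational products".

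The general safety sections place causality elsewhere. Under 7.1.1.1 the assessment of an AE's "relationship to study product will be done by the study clinician licensed to make medical diagnoses and listed on the Form FDA 1572", meaning the site PI or a sub-investigator. Section 7.1.3 says the same for SAEs, naming a licensed study physician in either of those roles. The Medical Monitor belongs to DMID, which is the sponsor (sections 1 and 2.1). The SAP does not restate or alter the halting rules.

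**The concern.** The person who must judge whether an SAE is related is not the person whose judgement stops dosing. If the two agree, this does not matter. If the site physician considers a non-fatal SAE vaccine-related and the Medical Monitor does not, the SAE bullets of 7.6.2 and 7.6.3 are not met. In a first-in-human trial of CJCV2, with or without ALFQ, the other subjects could then continue to receive doses while the disagreement is resolved.

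Elsewhere the protocol tends to let either party act. Seriousness can be declared by the site PI or the sponsor (7.1.3), and an individual can be removed by an investigator or the medical monitor (7.6.4). The PI's concurrence is also needed to resume after a halt (7.6.3), yet the PI's view alone does not start one for an SAE.

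**Working it through.** No figure in the plan bears on this point, so the check is mainly textual.

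**1. Triggers that depend on relatedness.** Sections 7.6.1 to 7.6.3 contain six such bullets: three for SAEs and three for Grade 3 unsolicited AEs. The Grade 3 bullets are:

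- sentinel: "Any Grade 3 unsolicited AE related to the investigational products"; one event is enough;
- cohort: "Two (2) or more subjects in the same cohort experience the same or similar Grade 3 unsolicited AE", judged related;
- study: "Three (3) or more subjects experience the same or similar Grade 3 unsolicited AE", judged related.

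Only two of the six name the Medical Monitor: the SAE bullets of 7.6.2 and 7.6.3.

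**2. One disputed event traced through the rules.** Take a non-fatal SAE that only the site calls related, in a non-sentinel, or in a sentinel outside the 7.6.1 window (first vaccination through Day 8, at any dose).

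- 7.6.1 does not apply, because the event is outside its scope.
- The SAE bullets of 7.6.2 and 7.6.3 are not met, because the Medical Monitor does not consider it related.
- The Grade 3 bullets of 7.6.2 and 7.6.3 are not met, because they need at least two or three subjects.
- The suspension clause of 7.6.3 is permissive. Its example is "an overall pattern of symptomatic, clinical, or laboratory events that the Medical Monitor considers related to the study products", so it too looks to the Medical Monitor.

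A death halts regardless. This is explicit in 7.6.3, where the relatedness condition attaches to the SAE only.

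**3. What does happen to that event.**

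- 4.1.3: the affected subject receives no further vaccinations.
- 7.1.3: SAEs get periodic SMC review unless related. The same list gives relatedness to the site physician, so the site's call most naturally moves the SAE out of the periodic cycle.
- 7.7 and SAP 4.1: the SMC is to meet ad hoc for immediate concerns or other safety concerns, including concerns noted by the SRC, on which the PI sits.
- 7.3.1: the Medical Monitor assesses every SAE for its impact on subject safety and protocol conduct.
- 4.1.3 item 13, 4.2.1 and 4.2.3: the PI can decline a dose for any subject, an investigator can discontinue any subject, and termination by the investigator is foreseen.

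None of these states that the other subjects' dosing pauses in the meantime.

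**4. Who falls under the rule.** Non-sentinels: 3 cohorts × 14 = 42, and 42/60 = 70%. Sentinels: 3 × 6 = 18, affected only outside their window. These are counts of people covered, not of expected events.

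**5. How rare related SAEs may be.** CJCV1 had 0 vaccine-related SAEs in 48 subjects (3.1.1). The exact 95% upper limit is 1 − 0.025^(1/48) = 0.074, or 7.4%. No ALFQ-associated SAEs were reported in the malaria studies (3.1.2), with no denominator given. Both are different products, and both count all related SAEs, not disputed ones.

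**6. Illustration on assumed values.** Let p be the chance per subject of an SAE that the site calls related, and c the chance that the Medical Monitor concurs. Neither is in the documents. Apply the 7.6.2 rule to all 20 subjects of a cohort, ignoring the sentinel window. The chance of at least one triggering SAE is 1 − (1 − pc)^20 now and 1 − (1 − p)^20 with an either-assessor rule.

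| p | c | now | either assessor |
|---|---|---|---|
| 1% | 0.8 | 14.8% | 18.2% |
| 1% | 0.5 | 9.5% | 18.2% |
| 5% | 0.8 | 55.8% | 64.2% |
| 5% | 0.5 | 39.7% | 64.2% |

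At c = 1 the two rules coincide. The size of the gap depends entirely on p and c.

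**The case against.** The strongest reply is that there is no contradiction. Sections 7.1.1.1 and 7.1.3 say who records causality, while 7.6.2 and 7.6.3 say whose judgement stops the trial. A sponsor may reasonably give these to different people, and the Medical Monitor's mandatory review under 7.3.1 fits the second role. The looser sentinel wording also fits a graded design in which early rules are the most sensitive. This stands: the present wording is a design choice, not an error.

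The second reply is that the practical gap is narrow. At a single site, the Medical Monitor would have to disagree, the PI would have to keep dosing despite a related call from the site, and the SMC would have to leave dosing running. This also stands, and it limits the importance of the point. It does not remove it, because each of those safeguards relies on someone choosing to act, whereas a halting rule takes effect by itself.

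A reader might infer more than the text supports in two ways. One is that a site-related SAE is left to routine periodic SMC review; 7.1.3 most naturally says the opposite. The other is that continued dosing is simply at the sponsor's discretion. The Medical Monitor's assessment is required, and site concerns have a stated route to an SMC meeting that does not need the Medical Monitor's agreement.

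**Conclusion.** The point holds as a cheap improvement. For a single non-fatal SAE outside the sentinel window, no provision obliges a pause for the other subjects when only the site physician considers the event related. Existing controls bring the event to the SMC and stop the affected subject's doses, so what is missing is limited to the interval before the SMC acts.

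The expected effect is small. It requires a related SAE, which is probably rare, and disagreement about it, for which the documents give no rate. They also give no duration for an SMC review, so the number of doses at stake cannot be stated. The conclusion rests on reading 7.1.3 as sending site-related SAEs to non-periodic review, and on the SMC charter and MOP, which are not available here, adding no automatic pause.

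**What to change.** In the SAE bullets of 7.6.2 and 7.6.3, write: *any SAE considered related by the site investigator or the Medical Monitor*. Leave 7.6.1 alone, since it names no assessor, and leave the Grade 3 bullets as they are. Carry the phrase into the SMC charter or MOP if they repeat the rules. The SAP is unaffected.

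The change cannot loosen any rule. Its cost is an occasional extra pause pending SMC review, possibly on one sub-investigator's call under the reasonable-possibility standard of 7.1.1.1. The Day 29 and Day 57 visits allow only +2 days (5.3.3), so a pause could push some doses out of window and remove later data from the per-protocol population (9.4.1).

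SAP 4.3 describes all three cohorts as already enrolled. If dosing is complete, the change matters mainly for the follow-on studies foreseen in Protocol 9.2, should these rules be reused. If the sponsor prefers the present rule, a sentence explaining why the designated assessor's judgement does not trigger the halt would suffice.

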7.6.3 Study Halting Criteria

Further study enrollment and dosing will be halted for SMC review/recommendation if any of the following Halting Rules are met after administration of any dose of study product.

- Death of an enrolled subject or any SAE if the SAE is considered by the Medical Monitor to be related to the investigational products.
- Three (3) or more subjects experience the same or similar Grade 3 unsolicited AE (including but not limited to the same parameter or next level of coding in the MedDRA hierarchy, High Level Term per the MedDRA current version) related to the investigational products.

Three (3) or more subjects experience the same Grade 3 solicited AE. The size (as measured in mm) of erythema, ecchymosis, and induration/swelling will not be used as a halting criterion

If a halting rule is met, a thorough review of the event will be undertaken by the investigators and the SMC. Vaccination may be resumed with the concurrence of the SMC, sponsor's representative, and the PI.

The study may also be suspended because of safety findings such as an overall pattern of symptomatic, clinical, or laboratory events that the Medical Monitor considers related to the study products and that may appear minor in terms of individual events, but that may collectively represent a serious potential concern for safety

7.6.4 Individual Halting Criteria

A subject may be removed from the study if an investigator or medical monitor deems it in the best interest of the subject. A subject also may halt (discontinue participation) at any time. If a subject meets an individual halting criterion, it will not halt the study but halt the subject's involvement.

7.7 Safety Oversight by SMC

Safety oversight will be conducted by a Safety Monitoring Committee (SMC) which is an independent group of experts that advises the DMID. The primary responsibility of the SMC is to monitor subject safety. The SMC is external to the DMID and comprises at least 3 voting members. The SMC will consist of members with appropriate phase 1 study expertise to contribute to the interpretation of the data from this trial. Its activities will be delineated in a SMC charter that will describe the membership, responsibilities, and the scope and frequency of data reviews. The SMC will operate on a conflict-free basis independently of the study team. The DMID or the SMC may convene ad hoc meetings of the SMC according to protocol criteria or if there are concerns that arise during the study.

As defined in the charter, the SMC will meet before the initiation for the study and ad hoc as required due to occurrence of a safety event when a halting rule is met or for immediate concerns regarding observations during this study.

8 HUMAN SUBJECTS PROTECTION

8.1 Institutional Review Board/Independent Ethics Committee

The site PI will obtain IRB approval for this protocol to be conducted at his/her research site(s) and send supporting documentation to the DMID before initiating recruitment of subjects. The investigator will submit applicable information to the IRB/IEC on which it relies for the review, to conduct the review in accordance with 45 CFR 46, ICH E6 GCP, and as applicable, 21 CFR 56 (Institutional Review Boards) and 21 CFR 50 (Protection of Human Subjects), other federal, state, and local regulations. The IRB/IEC must be registered with OHRP as applicable to the research. DMID must receive the documentation that verifies IRB/IEC-approval for this protocol, associated informed consent documents, and upon request any recruitment material and handouts or surveys intended for the subjects, prior to the recruitment and enrollment of subjects.

Any amendments to the protocol or consent materials will be approved by the IRB/IEC before they are implemented. IRB/IEC review and approval will occur at least annually throughout the enrollment and follow-up of subjects and may cease if annual review is no longer required by applicable regulations and the IRB/IEC. The investigator will notify the IRB/IEC of deviations from the protocol and reportable SAEs, as applicable to the IRB/IEC policy.

Each institution engaged in this research will hold a current FWA issued by the OHRP for federally funded research.

Informed Consent Process

Informed consent is a process that is initiated prior to an individual agreeing to participate in a trial and continuing throughout the individual's trial participation. Before any study procedures are performed, informed consent will be obtained and documented. Subjects will receive a concise and focused presentation of key information about the clinical trial, verbally and with a written consent form. The explanation will be organized and presented in lay terminology and language that facilitates understanding why one might or might not want to participate.

An investigator or designee will describe the protocol to potential subjects face-to-face. The key information about the purpose of the study, the procedures and experimental aspects of the study, risks and discomforts, any expected benefits to the subject, and alternative treatment will be presented first to the subject.

Subjects will also receive an explanation that the trial involves research, and a detailed summary of the proposed study procedures and study interventions/products. This will include aspects of the trial that are experimental, the probability for random assignment to treatment groups, any expected benefits, all possible risks (including a statement that the particular treatment or procedure may involve risks to the subject or to the embryo or fetus, if the subject is or may become pregnant, that are currently unforeseeable), the expected duration of the subject's participation in the trial, alternative procedures that may be available and the important potential benefits and risks of these available alternative procedures.

Subjects will be informed that they will be notified in a timely manner if information becomes available that may be relevant to their willingness to continue participation in the trial. Subjects will receive an explanation as to whether any compensation and any medical treatments are available if injury occurs, and, if so, what they consist of, or where further information may be obtained. Subjects will be informed of the anticipated financial expenses, if any, to the subject for participating in the trial, as well as any anticipated prorated payments, if any, to the subject for participating in the trial. They will be informed of whom to contact (e.g., the investigator) for answers to any questions relating to the research project.

Information will also include the foreseeable circumstances and/or reasons under which the subject's participation in the trial may be terminated. The subjects will be informed that participation is voluntary and that they are free to withdraw from the study for any reason at any time without penalty or loss of benefits to which the subject is otherwise entitled.

The extent of the confidentiality of the subjects' records will be defined, and subjects will be informed that applicable data protection legislation will be followed. Subjects will be informed that the monitor(s), auditors(s), IRB, NIAID, and regulatory authority(ies) will be granted direct access to the subject's original medical records for verification of clinical trial procedures and/or data without violating the confidentiality of the subject, to the extent permitted by the applicable laws and regulations, and that, by signing a written ICF, the subject is authorizing such access.

Subjects will be informed that records identifying the subject will be kept confidential, and, to the extent permitted by the applicable laws and/or regulations, will not be made publicly available and, if the results of the trial are published, the subject's identity will remain confidential. Subjects will be informed whether private information collected from this research and/or specimens will be used for additional research, even if identifiers are removed.

Subjects will be allowed sufficient time to consider participation in this research trial and can discuss this trial with their family, friends, or legally authorized representative, or think about it prior to agreeing to participate.

ICFs will be IRB-approved, and subjects will be asked to read and review the consent form. Subjects must sign the ICF prior to starting any study procedures being done specifically for this trial.

Once signed, a copy of the ICF will be given to the subject(s) for their records. The subject(s) may withdraw consent at any time throughout the course of the trial. The rights and welfare of the subject(s) will be protected by emphasizing to them that the quality of their medical care will not be adversely affected if they decline to participate in this study.

Study personnel may employ recruitment efforts prior to obtaining study consent if a patient-specific screening consent is on record or if the IRB has agreed that chart review is allowed without a fully executed screening consent. In cases where there is not a patient-specific screening consent on record, site clinical staff may pre-screen via chart review and refer potential subjects to the Research staff. Research staff would obtain written consent per the standard informed consent process before conducting protocol-specific screening activities.

New information will be communicated by the site PI to subjects who consent to participate in this trial in accordance with IRB requirements. The informed consent document will be updated, and subjects will be re-consented per IRB requirements, if necessary. Subjects will be offered a copy of all ICFs that they sign.

